9.1.2 Surgical Portion (includes pre-surgical dosing)

ABTC # 1801

NCI # ABTC-1801

PI: [name]

- 1- All baseline measurements must be done within minus 21 calendar days of treatment administration unless otherwise specified.
- 2- Including blood pressure, respiratory rate, heart rate, temperature, weight, height: height is required at baseline only; weight is required at pre-odd cycle evaluations only.
- 3- Including albumin, alkaline phosphatase, total bilirubin, calcium, creatinine, magnesium, phosphorus, potassium, SGOT, SGPT, sodium.
- 4- For women of child-bearing potential: monthly pregnancy tests through 6 months after completion of pamiparib (BGB-290) or temozolomide administration.
- 5- Within minus 5 calendar days of cycle start including Pre-Cycle 1. MRI does not need to be repeated if postsurgical MRI is within 21 days of Cycle 1 start. Please refer to the Imaging Core Manual for further imaging requirements and submission information.
- 6- Pre-surgery pamiparib (BGB-290) is administered twice daily for 7-9 days prior to scheduled surgery, including the day of surgery;

Post-surgery pamiparib (BGB-290) is administered orally twice daily on Days 1-28 of each 28-day cycle. See Section 4.5.1. Patients are required to keep a medication diary. Patients are required to keep a medication diary.

- 7– Post-surgery, temozolomide is administered once daily on according to the specified dose level of each 28-day cycle. See Section 4.5.2.
- 8– Evaluations done within +7 days of off treatment date unless indicated: do not repeat: if MRI within minus 14 days of off-treatment date (please refer to the Imaging Core Manual for further imaging requirements and submission information).; if H&P/neuro, KPS, labs within minus 5 days of off-treatment date.
- 9- If ANC < 1500 or plts < 100,000, CBCs/differentials will be repeated twice a week until counts are recovered (ANC ≥1500 or plts ≥100,000) per protocol. If counts are recovered (ANC ≥1500 or plts ≥100,000) on day of scheduled drawing do not repeat until next protocol schedule day

- 10- Adverse Events must be followed for at least 30 days from last dose of pamiparib (BGB-290).
- 11-Perform within +14 days of the 30-day post-last dose date.
- 12– Archived tumor tissue from a prior resection for glioma, preferably from the initial diagnosis, will be collected from patients. See Section 9.5.1.
- 13– Blood samples will be obtained for pharmacokinetics at baseline (prior to first pre-surgical dose), and shortly before and after surgical resection. Section 9.5.2.
- 14-Fresh tumor tissue for drug concentration will be collected day of surgery. See Sections 9.5.2.
- 15- Patient should be seen on the day of surgery (prior to surgery) to evaluate for AEs.
- 16– Within 3 days post-surgery.
- 17- Perform within minus 7 days of first dose.
- 18-± 1 day
- 19- In subjects whose CBC, Diff, Platelets have been stable through the first 6 cycles, the frequency of hematologic testing can be reduced to a q2 weeks schedule (Day 15 of every cycle and Pre-cycle evaluation) starting in Cycle 7. CBC, Diff, Platelets will be considered "stable" if the following criteria are met: 1) No reports of ANC<1500/µl in ANY of the Cycles 1-6 weekly Labs and 2) No reports of Platelets<100,000/µl in ANY of the Cycles 1-6 weekly Labs. If at any point during treatment on the revised q2 weeks schedule the above mentioned ANC and Platelets criteria are not met, CBC, Diff, Platelets should be repeated twice a week until counts are recovered (ANC ≥1500 or Platelets ≥100,000). Once counts are recovered, the schedule of CBC, Diff, Platelets should go back to, and stay at, weekly monitoring (NOT q2 weeks).

IMPORTANT: The guidance below is subject to applicable local Institutional Policy on telemedicine. In the event that local Institutional Policy regarding telemedicine differs from this guidance, then please follow local Institutional Policy.

Telemedicine visits may be substituted for in person clinical trial visits or portions of clinical trial visits where determined to be appropriate and where determined by the investigator not to increase the participants risks. Prior to initiating telemedicine for study visits the study team will explain to the participant, what a telemedicine visit entails and confirm that the study participant is in agreement and able to proceed with this method. Telemedicine acknowledgement will be obtained in accordance with the Guidance for Use of Telemedicine in Research. In the event telemedicine is not deemed feasible, the study visit will proceed as an in-person visit. Telemedicine visits will be conducted using HIPAA compliant method approved by the Health System and within licensing restrictions.

Additionally, informed consent should be obtained in person, but if deemed necessary, via telemedicine.

ABTC # 1801

NCI # ABTC-1801

PI: [name]

9.2 Adverse Events

Patients will be evaluated for safety if they have received at least one dose of pamiparib (BGB-290).

The timely reporting of AEs (including deaths) is required by the U.S. Food and Drug Administration. The reporting of toxicities is part of the data reporting for this study. Adverse events will be collected for at least 30 days following the last dose of study drug. Beyond this time point only newly occurring adverse events that are serious and drug-related will be recorded.

Adverse events must be reported to the ABTC Central Office and the NCI by the investigative site in the manner described and per the requirements of the clinical site's IRB.

Adverse events will be entered into CTEP's iMedidata Rave database by the investigative site in a timely manner. See Section – Data Collection/Reporting.

9.2.1 Adverse Events and Potential Risks

9.2.1.1 Adverse Events and Potential Risks with Pamiparib (BGB-290) in combination with Temozolomide

As of 18 June 2021, a total of 208 patients have received pamiparib with temozolomide. The most common pamiparib and/or temozolomide side effects reported by these patients are listed below. In most patients, the side effects were mild and responded to treatment. In some patients, the side effects were long-lasting, serious, or required urgent treatment. Some side effects may be life-threatening or fatal.

The side effects are adapted from Section 5.2.5.2 (Treatment-Emergent Adverse Events Assessed as Related to Study Treatment) for the pamiparib plus TMZ combination pool in the Pamiparib Investigator's Brochure (IB) Edition 7. The term "side effect" implies causality.

Adverse Drug Reactions

See the Informed Consent and Investigator Brochure for the risk tables.

9.2.1.2 Known Potential Toxicities of Temozolomide

Known potential toxicities of temozolomide are hematological toxicities (leucopenia, lymphopenia, thrombocytopenia, and anemia), renal insufficiency, nausea and vomiting, liver enzyme abnormalities, lethargy, rash, headache, alopecia, constipation, fatigue/malaise, anorexia, hyperglycemia and diarrhea are known toxicities. Recently, cases of hepatic injury, including fatal hepatic failure, have been observed in patients enrolled in clinical studies utilizing the agent temozolomide. In addition, it was noted that

NCI # ABTC-1801

PI: [name]

liver toxicity may occur several weeks or more after initiation of treatment or after temozolomide discontinuation. Refer to the package insert for additional information on adverse events observed to date.

Rats given temozolomide in recent multidose toxicity studies have developed adenocarcinoma of the breast, fibrosarcomas, malignant Schwannomas (a variant of fibrosarcoma), keratoacanthomas and basal cell adenomas. Similar studies conducted in dogs did not reveal any similar findings. The significance of this finding for humans is not known presently.

Temozolomide is potentially mutagenic and should be handled with appropriate precautions by both staff and subjects. Subjects with known or suspected hypersensitivity to temozolomide should not be treated with temozolomide. There are no data available on the effect or management of temozolomide overdose.

Additional information is available in the temozolomide package insert (www.temodar.com)

9.2.2 Adverse Event Characteristics

Definition - Adverse Event (AE)

Adverse event is defined as any unfavorable and unintended sign (including an abnormal laboratory finding), symptom or disease temporally associated with the use of a medical treatment or procedure regardless of whether it is considered related to the medical treatment or procedure (attribution of unrelated, unlikely, possible, probable, or definite).

Recording of Adverse Events - ABTC AE Form

- The investigator will monitor each patient closely for the development of adverse events and record all such events on the ABTC AE Case Report Form. Each single sign or symptom must be reported separately.
- CTCAE term (AE description) and grade: The descriptions and grading scales found in the revised NCI Common Terminology Criteria for Adverse Events (CTCAE) version 5.0 will be utilized for AE reporting. All appropriate treatment areas should have access to a copy of the CTCAE version 5.0. A copy of the CTCAE version 5.0 can be downloaded from the CTEP web site (http://ctep.cancer.gov/protocolDevelopment/electronic_applications/ctc.htm). You must use one of the CTCAE criteria to define your event.

Adverse events not included in the CTCAE should be reported under "Other" within the appropriate category and graded 1 to 5 according to the general grade definitions mild, moderate, severe, life-threatening, fatal or disabling - as provided in the CTCAE or the CTCAE Manual. New adverse events may be submitted to the CTEP Help Desk at [contact] for annual evaluation by the CTCAE Change Management Committee.

PI: [name]

- Attribution of the AE: The investigator will be asked to document his/her opinion of the relationship of the event to study medication as follows:
 - *Unrelated* The AE is clearly not related to the investigational agent(s).
 - Unlikely The AE is doubtfully related to the investigational agent(s).
 - *Possible* The AE may be related to the investigational agent(s).
 - *Probable* The AE is most likely related to the investigational agent(s).
 - *Definite* The AE is clearly related to the investigational agent(s).
- All adverse events should be followed up in accordance with good medical practice. Abnormalities of laboratory events which, in the opinion of the investigator, constitute adverse events (even if not serious) should be followed.

9.3 Serious Adverse Events and Expedited Adverse Event Reporting

9.3.1 Definition – Serious Adverse Event (SAE)

An adverse event is considered serious if it results in ANY of the following outcomes:

- 1) Death
- 2) A life-threatening adverse event
- An adverse event that results in inpatient hospitalization or prolongation of existing hospitalization for ≥ 24 hours
- 4) A persistent or significant incapacity or substantial disruption of the ability to conduct normal life functions
- 5) A congenital anomaly/birth defect
- 6) Important Medical Events (IME) that may not result in death, be life threatening, or require hospitalization may be considered serious when, based upon medical judgment, they may jeopardize the patient or subject and may require medical or surgical intervention to prevent one of the outcomes listed in this definition.

9.3.2 Expedited Adverse Event Reporting

> Use CTEP-AERS Web Application and Document on ABTC AE Form

- All SAEs must be documented on both the ABTC AE form and using the CTEP-AERS Web Application within 24 hours of learning of the event.
- Expedited AE reporting for this study must use CTEP-AERS (CTEP Adverse Event Reporting System), accessed via the CTEP web site (https://eapps-ctep.nci.nih.gov/ctepaers). In the rare occurrence when Internet connectivity is lost, a 24-hour notification is to be made to the ABTC Central Office by telephone at [contact] or [contact] or [contact]. Once Internet connectivity is restored, the 24-hour notification must be entered electronically into CTEP-AERS by the original submitter at the site.

ABTC # 1801

NCI # ABTC-1801

PI: [name]

- ABTC will be notified automatically when an SAE is reported through CTEP-AERS (within 24 hours). All SAEs will be documented and tracked by the ABTC Central Office. Queries and follow up required for completing all SAEs will be conducted through the ABTC Central Office in a timely fashion. When an expedited report is required (7 or 15 days), a speedy resolution of queries will be expected in order to allow for on-time reporting to the FDA. BeiGene is responsible for reporting all applicable SAEs to the FDA.
- CTEP-AERS is programmed for automatic electronic distribution of reports to the following individuals: Principal Investigator and Adverse Event Coordinator(s) of the Adult Brain Tumor Consortium (ABTC), the local treating physician, and the Reporter and Submitter. CTEP-AERS provides a copy feature for other e-mail recipients.
- The ABTC Central Office is responsible for submitting to the CTSU documentation of AEs that they deem reportable for posting on the CTSU protocol web page and inclusion on the CTSU bi-monthly broadcast.
- Expedited Reporting Guidelines

Use the NCI protocol number and the protocol-specific patient ID provided during trial registration on all reports.

Note: A death on study requires both routine and expedited reporting regardless of causality, unless as noted below. Attribution to treatment or other cause must be provided.

Death due to progressive disease should be reported as Grade 5 "Disease progression" in the system organ class (SOC) "General disorders and administration site conditions. Evidence that the death was a manifestation of underlying disease (*e.g.*, radiological changes suggesting tumor growth or progression: clinical deterioration associated with a disease process) should be submitted.

9.3.3 Other SAE Reporting

Any Serious Adverse Event, as described in Section 9.3.1, including death due to any cause, which occurs during this study must be **reported immediately (within 24 hours)** to the ABTC Central Office.

A phone call must be made to:

[name] ABTC DATA COORDINATOR OFFICE: [contact] [contact]

ABTC # 1801

NCI # ABTC-1801

PI: [name]

OR [name], ABTC MANAGER: [contact] / [contact]

These events also must be reported by the investigator to the appropriate Institutional Review Board (IRB).

Patients who are removed from study due to adverse events should be followed until the adverse event has resolved or stabilized. Copies of relevant documentation, such as laboratory reports, should be kept with the patient's study records.

Secondary Malignancy

A secondary malignancy is a cancer caused by treatment for a previous malignancy (e.g., treatment with investigational agent/intervention, radiation or chemotherapy). A secondary malignancy is not considered a metastasis of the initial neoplasm.

Any secondary malignancies that occur following treatment with pamiparib (BGB-290) should be reported via CTEP-AERS. Three options are available to describe the event:

- Leukemia secondary to oncology chemotherapy (e.g., acute myelocytic leukemia [AML])
- Myelodysplastic syndrome (MDS)
- Treatment-related secondary malignancy

Any malignancy possibly related to cancer treatment (including AML/MDS) should also be reported via the routine reporting mechanisms outlined in Section 12.0.

Second Malignancy

A second malignancy is one unrelated to the treatment of a prior malignancy (and is NOT a metastasis from the initial malignancy). Second malignancies require ONLY routine reporting via CDUS unless otherwise specified.

9.4 Routine Adverse Event Reporting

All Adverse Events **must** be reported in routine study data submissions. **AEs reported expeditiously through CTEP-AERS must** also be reported in routine study data submissions (Section 12.4).

Adverse event data collection and reporting, which are required as part of every clinical trial, are done to ensure the safety of patients enrolled in the studies as well as those who will enroll in future studies using similar agents. AEs are reported in a routine manner at scheduled times during the trial using Medidata Rave. For this trial the Adverse Event CRF is used for routine AE reporting in Rave.

ABTC # 1801

NCI # ABTC-1801

PI: [name]

9.5 Correlative Studies

Exploratory biomarker and correlative studies are focused on identifying key molecular correlates of treatment response. A subset of patients will be accrued to a surgical component of the study in which pamiparib (BGB-290) is administered prior to re-resection to assess intra-tumoral drug levels.

30 unstained FFPE slides are required for all patients enrolled on this study, typically from the initial diagnosis specimen. Exceptions will be made in cases where there is limited tissue, upon approval by the study Chairs. All samples, including blood and tissue, will be sent to the [name] laboratory for distribution to the study collaborators.

9.5.1 Archival Tumor Tissue (all patients)

2HG Quantification

Quantification of 2HG in archival FFPE specimens via LC-MS detection and correlation with treatment response will be performed in collaboration with [name] (Pharmacology Core, Karmanos Cancer Institute [KCI], Wayne State University School of Medicine), using optimized protocols developed by Li and [name].

Response Correlation with 2HG, Somatic Alterations, Gene Expression/Methylation Patterns

Response correlation with 2HG, somatic alterations, and gene expression/methylation patterns in FFPE tumor tissue will be performed in collaboration with the Translational Genomics Research Institute (TGen). TGen investigators have participated in the initial TCGA efforts to sequence glioblastoma ³³. Subsequently, prospective precision medicine trials in recurrent adult GBM (NCT02060890) and pediatric DIPG (NCT02274987) demonstrate core competencies to support correlative trials. Sequencing pipelines developed at TGen have also been utilized for identification of genomic signatures of vulnerability in adult GBM patients via a retrospective analysis ³⁴.

Archival FFPE Slide Preparation and Shipping Requirements:

Each submitting institution should submit 30 unstained sections from a previous surgery for glioma, preferably the initial diagnosis specimen, 5 microns thick, mounted on standard glass microscope slides.

Tissue Specimens should be mailed according to these instructions:

1. Label the samples with the following information:

ABTC Protocol Number (ABTC 1801) Description (FFPE slides) Patient Study ID Number Date of Collection Time of Collection

ABTC # 1801

PI: [name]

- 2. Complete the "shipping manifest for research specimen collection and shipping" (see SOP/Lab Manual)
- 3. Place the FFPE slides in a plastic zip lock bag and wrap in bubble wrap or another type of padded material prior to shipping. The zip lock bag can be placed into a FedEx envelope or small shipping box.
- 4. Verify that the FedEx air bill is marked Standard Overnight Shipping.
- 5. Call Courier Service to pick up specimens.
- 6. Ship overnight (Mon-Thur). No shipments will occur over weekends or holidays. Prior to any shipment, please notify [name] via email and/or telephone. The samples will be shipped to the following address:

Laboratory of [name] c/o [name] Yale University School of Medicine [name] Email: [contact]

9.5.2 Brain Tissue Concentrations and Plasma Pharmacokinetics (Surgical Portion)

Tumor tissue pamiparib (BGB-290) levels, 2HG, and PARylation will be assessed in a patient subset treated with drug prior to re-resection (Surgical Portion), using optimized protocols in the Li group as noted in Section 9.5.1, and also based on methodology developed and validated in the [name] laboratory.

Blood samples for pharmacokinetics will be drawn at baseline (prior to first pre-surgical dose) and immediately before and after surgery. The PK sample drawn immediately before surgery must be taken following the Day 7 dose (which is taken 3-6 hours prior to surgery).

The concentration of pamiparib (BGB-290) will be determined in a 0.05-0.10 cm³ (50-100 mg) section of tumor tissue obtained from a contrast enhancing and non-contrast enhancing region of the tumor. Doses of pamiparib (BGB-290) should be taken at approximately the same time, in the morning, for 7 days (up to 9 days if surgery is delayed) with the last preoperative dose taken 3 to 6 hours prior to surgery.

Accurately record the time that the dose is taken prior to the tumor resection. The surgical procedure must be performed at least 3 hours but not longer than 8 hours after dosing. The biopsy specimens submitted for drug concentration determinations should be resected as close to 3-6 hours after dosing as possible, but not more than 8 hours after dosing.

Collection, preparation and shipping instructions for the frozen tissue specimens and the corresponding blood samples are provided in the study lab manual.

NCI # ABTC-1801

PI: [name]

10.0 OFF-TREATMENT/OFF-STUDY CRITERIA

Each subject has the right to withdraw from the study at any time without prejudice. The Investigator may discontinue any subject's participation for any reason, including AEs or failure to comply with the protocol (as judged by the Investigator, such as compliance below 80%, failure to maintain appointments, etc.).

Should a subject withdraw from the study, the reason(s) must be stated on the case report form and a final evaluation of the subject should be performed.

Patients who go off treatment must be followed for AEs for at least 30 days from the last dose of pamiparib (BGB-290).

10.1 Off-Treatment Criteria

- 1. Disease Progression: Remove patient from protocol therapy at the time progressive disease is documented. Disease progression is defined as: Progressive neurologic abnormalities not explained by causes unrelated to tumor progression (e.g. anticonvulsant or corticosteroid toxicity, electrolyte abnormalities, hyperglycemia, etc.) or a greater than 25% increase in the measurement of the tumor by MRI scan. If neurologic status deteriorates, on a stable or increasing dose of steroids, or if new lesions appear on serial MRI, further study treatment will be discontinued. Please refer to the Imaging Core Manual for further imaging requirements and submission information.
- 2. Adverse Event:
 - Intercurrent illness that prevents further administration of treatment
 - Patients who experience unacceptable toxicity. Patients removed from study for unacceptable adverse events will be followed until resolution or stabilization of the adverse event.
- 3. Patient Withdrawal: Patient's refusal to continue treatment: in this event, document the reason for withdrawal.
- 4. Non-Compliance: Failure to comply with protocol (as judged by the investigator such as compliance below 80%, failure to maintain appointments, etc.)
- 5. Physician Decision: If at any time the treating physician feels the constraints of this protocol are detrimental to the patient's health remove the patient from protocol therapy.

ABTC # 1801

PI: [name]

- 6. Protocol Defined Delay:
 - Patients will be off treatment who experience a treatment-related toxicity causing a delay in treatment >21 days. Note: Patients who experience grade 3 hepatic toxicity will be off treatment if treatment-is delayed >14 days.
 - Delay in protocol >28 days for major events or other non-treatment related delays
 - Patients who require >2 dose reductions
- 7. Death

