4.6.3 Corticosteroids

Postoperatively, corticosteroids should be tapered to a stable dose as determined by the clinical status of the patient. The lowest required steroid dose should be maintained throughout the duration of the study in order to eliminate steroid effects as a confounding variable in the interpretation of serial brain imaging studies. Corticosteroid doses can be tapered as clinically indicated if the patient appears to be responding to therapy as judged by serial scans. Corticosteroid dose may, of course, be increased in the event of clinical deterioration or at the discretion of the attending physician. In the event of suspected clinical deterioration, repeat brain imaging is recommended.

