
Progressive Disease – PD (defined by *any* of the following):

a) $\geq 25\%$ increase in sum of the products of perpendicular diameters of enhancing lesions compared to the smallest tumor measurement obtained either at baseline (if no decrease) or best response, on stable or increasing doses of corticosteroids.*

b) Significant increase in T2/FLAIR non-enhancing lesion on stable or increasing doses of corticosteroids compared to baseline scan or best response following initiation of therapy,* not due to co-morbid events (radiation therapy, demyelination, ischemic injury, infection, seizures, postoperative changes, or other treatment effects).

c) Any new lesion.

d) Clear clinical deterioration not attributable to other causes apart from the tumor (e.g., seizures, medication adverse effects, complications of therapy, cerebrovascular events, infection, etc.) or changes in corticosteroid dose. The definition of clinical deterioration is left to the discretion of the treating physician, but it is recommended that a decrease in 20% of KPS or from any baseline to 50% or less be considered, unless attributable to comorbid events.

- e) Failure to return for evaluation due to death or deteriorating condition.
- f) Clear progression of non-measurable disease.

* Stable doses of corticosteroids include patients not on corticosteroids.

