8.1.2 LGG RANO

Complete Response – CR (requires *all* of the following):

a) Complete disappearance of the lesion on T2 or FLAIR imaging (if enhancement had been present, it must have resolved completely);

b) no new lesions, no new T2 or FLAIR abnormalities apart from those consistent with radiation effects, and no new or increased enhancement;

c) patients must be off corticosteroids or only on physiological replacement doses;d) patients should be stable or improved clinically

Partial Response – PR (requires *all* of the following compared with the baseline scan):

a) greater than or equal to 50% decrease in the product of perpendicular diameters of the lesion on T2 or FLAIR imaging sustained for at least 4 weeks compared with baseline;

b) no new lesions, no new T2 or FLAIR abnormalities apart from those consistent with radiation effects, and no new or increased enhancement;

c) patients should be on a corticosteroid dose that should not be greater than the dose at time of baseline scan, and should be stable or improved clinically

PI: [name]

Minor Response – MR (requires *all* of the following):

a) a decrease of the area of non-enhancing lesion on T2 or FLAIR MR imaging between 25% and 50% compared with baseline;

b) no new lesions, no new T2 or FLAIR abnormalities apart from those consistent with radiation effect, and no new or increased enhancement;

c) patients should be on a corticosteroid dose that should not be greater than the dose at time of baseline scan, and should be stable or improved clinically

Stable Disease – SD (requires *all* of the following):

a) does not qualify for complete, partial, or minor response, or progression

b) stable area of non-enhancing abnormalities on T2 or FLAIR imaging;

c) no new lesions, no new T2 or FLAIR abnormalities apart from those consistent with radiation effect, and no new or increased enhancement; and

d) patients should be on a corticosteroid dose that should not be greater than the dose at time of baseline scan, and should be stable or improved clinically

Progressive Disease – PD (defined by *any* of the following):

a) development of new lesions or increase of enhancement (radiological evidence of malignant transformation);

b) a 25% increase of the T2 or FLAIR non-enhancing lesion on stable or increasing doses of corticosteroids compared with baseline scan or best response after initiation of therapy, not attributable to radiation effect or to comorbid events;

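### Section 10.1 stops treatment for tumor growth above 25% without the steroid condition that Section 8.1 attaches to progression, and in Phase I Sections 4.1 and 8.1 choose the RANO set by different rules

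*Combined protocol and SAP*

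**What the plan says.** Section 10.1, item 1, opens with "Remove patient from protocol therapy at the time progressive disease is documented". It then defines progression as neurologic worsening not explained by other causes, or "a greater than 25% increase in the measurement of the tumor by MRI scan". It does not refer to Section 8.1. The only steroid condition in the item comes in the next sentence and belongs to neurologic status: "If neurologic status deteriorates, on a stable or increasing dose of steroids, or if new lesions appear on serial MRI".

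Section 8.1 sets the study's assessment criteria. For enhancing disease (8.1.1, PD criterion a), growth is measured against the smallest tumor, "either at baseline (if no decrease) or best response, on stable or increasing doses of corticosteroids". Criterion b carries the same condition: "Significant increase in T2/FLAIR non-enhancing lesion on stable or increasing doses of corticosteroids". For non-enhancing disease (8.1.2, PD criterion b), progression is "a 25% increase of the T2 or FLAIR non-enhancing lesion on stable or increasing doses of corticosteroids compared with baseline scan", or compared with best response.

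Section 4.6.3 permits dose reduction on study: "Corticosteroid doses can be tapered as clinically indicated if the patient appears to be responding to therapy as judged by serial scans".

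For Phase I, Section 4.1 continues treatment until progression by LGG RANO or standard RANO, with the set chosen by tumor grade. Section 8.1 assigns HGG RANO to patients with measurable enhancing disease and LGG RANO to those with T2/FLAIR abnormality only. The recurrence definition in Section 3.2, which covers Phase I, also goes by enhancement.

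**The concern.** The protocol has two definitions of progression, and they can disagree about the same scan. Section 4.6.3 itself treats steroid effects as a confounder of serial imaging, which is why a steroid condition belongs with a growth threshold. Without it, apparent growth after a dose reduction ends therapy. The patients exposed include those who seemed to be responding, because they are the ones Section 4.6.3 says may be tapered. CR also requires being off corticosteroids or on physiologic replacement only, so a patient on a higher dose has to taper to qualify for it.

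In Phase I there is a second ambiguity. Two sections give different rules for which RANO set decides whether a patient may continue.

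**Working it through.** The check is a comparison of rules. The lesion sizes below are illustrations, not data from the documents.

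**1. The growth rules side by side**

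| Element | 10.1 item 1 | 8.1.1 PD a | 8.1.2 PD b |
|---|---|---|---|
| Threshold | above 25% | 25% or more | 25% |
| Measured on | tumor on MRI, dimension not given | enhancing lesions, bidimensional | T2/FLAIR lesion |
| Comparator | not given; 8.2 supplies the smallest scan to date | baseline or best response | baseline or best response |
| Steroid condition | none | stable or increasing dose | stable or increasing dose |

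The thresholds are practically the same. The difference that matters is the last row.

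**2. Enhancing disease**

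Take a tumor of 20 cm² at baseline, 10 cm² at its smallest and 13 cm² now. The steroid dose was reduced between the last two scans. There is no new lesion, T2/FLAIR is stable and the patient is clinically stable.

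- Change from smallest: 13/10 − 1 = +30%.
- Change from baseline: (20 − 13)/20 = 35% below baseline.
- Section 10.1: 30% exceeds 25%, so treatment stops.
- Section 8.1.1: criterion a fails because the dose was falling, and the stated conditions exclude the other PD criteria. The scan is not PD and fits the stable-disease definition there.

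**3. Non-enhancing disease**

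Take a FLAIR product that goes from 20 to 26 cm², with the dose reduced between the scans, no new lesion, no increase in enhancement and a clinically stable patient.

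- Change: 26/20 − 1 = +30%.
- Section 10.1: treatment stops.
- Section 8.1.2: criterion b is not met, so the scan is not PD. It is not clearly stable disease either, because that category asks for a stable non-enhancing area. This case shows only that the scan is not PD.

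**4. Timing of the taper**

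The two rules part only if the dose falls between the smallest scan and the growth scan. If the taper ended earlier and the dose was then unchanged, the dose is arguably stable and both rules give progression.

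**5. Choice of RANO set in Phase I**

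Phase I takes WHO grades II to IV, so grade and enhancement can disagree.

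| Patient | Set under 8.1 | Set under 4.1 |
|---|---|---|
| Grade II, measurable enhancement | HGG RANO | LGG RANO, if grade II maps to it |
| Grade IV, T2/FLAIR abnormality only | LGG RANO | standard RANO, if grade IV maps to it |

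Section 4.1 does not map grades to sets; the right-hand column is the natural reading. The population is the 6 to 18 Phase I patients in Section 3.1, and only those with discordant features are affected. The DLT window is 28 days and the first on-study MRI comes before cycle 3, so the MTD decision is not involved. Sections 4.2 and 4.3 contain no grade rule.

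**The case against.** The strongest reply is that a stopping rule may legitimately be broader than endpoint progression, and that experienced sites will apply RANO anyway. The first part would hold if 10.1 were labelled as a separate stopping rule. Instead it presents its wording as the definition of disease progression. Section 4.1 names RANO progression as the Phase I trigger and refers to 10.1 for the other reasons to stop. The second part is an argument for writing RANO into 10.1.

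It is also fair to say that the case is narrow. Section 4.6.3 links tapering to apparent response, and growth above 25% must then follow within that taper. This stands, and it limits the size of the point.

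Four stronger readings are tempting, and the documents do not support them:

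- *Section 10.1 fails to stop patients who progress through increased enhancement or T2/FLAIR change.* Its opening words, "Remove patient from protocol therapy at the time progressive disease is documented", probably cover them.
- *A stop under 10.1 dates the PFS event.* Section 11 does not name the criteria for PFS or duration of response, but RANO under Section 8.1 is the natural reading. Section 10.2 continues progression follow-up after treatment ends.
- *The Phase I conflict biases PFS.* Section 1.2 sets the PFS objective for Arms A and B, and Section 11 lists the secondary endpoints under Phase II.
- *Slight growth of existing enhancement in a grade II tumor is definitely PD under one set and not the other.* That needs the assumed grade mapping and a judgement on whether the change meets the LGG criterion, which speaks of malignant transformation.

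The Imaging Core Manual was not available. Section 10.1 cites it for imaging and submission requirements, not for a definition of progression.

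**Conclusion.** The point holds and is minor. Followed literally, Section 10.1 removes from treatment a patient whose scan is not progression under Section 8.1. This requires more than 25% growth from the smallest scan, a dose reduction between the two scans, no new lesion, stable clinical status and, for enhancing disease, stable T2/FLAIR; for non-enhancing disease, no increase in enhancement. In Phase I, Sections 4.1 and 8.1 can also assign different criteria to a patient whose grade and enhancement disagree. That affects only whether the patient continues treatment, not the Arm A and B endpoints.

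The documents give no basis for a frequency, so none is offered. A reader might infer that the primary result is at risk. The CR+PR definition is tied to Section 8.0 and does not depend on 10.1, and the sample size and decision rules are unchanged. The conclusion concerns the protocol text and does not claim that sites applied it literally.

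**What to change.** - **Section 10.1, item 1:** replace the definition with *PD per Section 8.1*. If a broader trigger is wanted, label it a treatment-discontinuation rule that does not date PFS.
- **Section 4.1:** choose the RANO set by measurable enhancement at baseline, as Section 8.1 does.
- **Section 11 (optional clarification):** state that PFS and duration of response use PD per Section 8.1.

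The cost is about one sentence in each place. No new scans, data or patients are needed: the schedule in Section 9.1 already records glucocorticoid dose at the scheduled MRI time points, so the steroid condition can be applied with what is collected. The change would not settle how Section 8.1.2 classifies the non-enhancing case, which is neither PD nor clearly stable disease, but it would settle whether treatment stops.
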